5.2 Recruitment Methods

- **Phase 1 (Focus group):** Potential participants will be sent a letter from the MPLS VA explaining the project and providing an opt-out option. Within two weeks the study coordinator and/or the research assistant will attempt to contact them by phone and asked if they would be interested in participating in a 60-90minute group discussion on their opinions about a study on reducing pain through walking. The call will include reviewing information that will be contained in the consent form. The study coordinator and research assistant will attempt to call the participants for a maximum of 6 times at different times of the day. The recruitment sample focus groups will be restricted to black patients from the Atlanta VAMC, selected from the CDW (who will then be excluded from the study sample). At the time of the focus groups the participant will be presented with the consent form. The participant will be given time to read the form. Key aspects of the form will also be reviewed verbally, including that (1) the focus group is expected to last 60-90 minutes (2) they will be audiotaped (3) the information they provide will be de-identified prior to analysis (4) they may skip any questions or terminate the interview at any time if they wish 5) and it will not affect their care at the VA if they choose not to participate. Only participants signing an informed consent form will be interviewed. All focus groups will be conducted in the Atlanta VAMC by [name], PI.
- In month 2 of the study we will conduct two patient focus groups to refine the recruitment materials (recruitment letter, brochure, recruitment scripts), the instructions related to use of pedometers, and counselor communication strategies, and to collect additional information on barriers to walking. In study month 4, we will conduct two additional patient focus groups to obtain feedback on modified versions of these materials, based on input from the first two focus groups.

- Initially we used Olympus digital voice recorders, which had been approved by MPLS ISO for use. Once the Olympus voice recorders were no longer supported by VA OIT, encrypted Philips DCM Digital Voice Recorders were purchased and used for recording. The voice recorders are VA equipment tracked via bar code by the MPLS facility inventory specialist. The ISO has worked with the PI to establish local procedures for use of the recorders, which are kept in a locked safe when not in use and are logged in and out prior to and after interviews. Once the interview is complete and a recording has been made on the device, the interviewers will promptly transfer the recording to the established secured VA server space and the recordings will be erased from the device. At the end of their life cycle the digital recording devices will follow electronic media sanitation procedures under the guidance of the MPLS ISO. This same procedure is used in C-IRB #12-28.
- **Phase 2 Pilot:** Recruitment methods for the Phase 2 Pilot will be kept the same as Phase 2 recruitment methods, differing only in that we are recruiting and enrolling 3 participants for the Pilot.
- **Phase 2:** We will use the 14 ICD9 (and ICD10 code conversions) that capture the most commonly used chronic pain codes to identify 1,000 patients with Musculoskeletal Diagnoses within the past 12 months, who are identified as Atlanta VAMC patients. Potentially eligible patients will be mailed a letter from the Minneapolis VAMC describing the study, providing an opt-out option, and informing them that they will be contacted by phone. Along with the letter will be an information sheet containing elements of informed consent. All patients will then be called by a trained interviewer, who will be the study coordinator and/or the RAs (from the Minneapolis VA) approximately a week or two after the letter is sent out, who will ask if they received the letter about the study and will briefly tell them about the purpose and the opportunity to participate. We will use the same call protocol described in phase 1. If they are interested, the interviewer will ask them 12 screening questions. If eligible, they will be invited to participate in the study and the interviewer will review the information sheet and obtain verbal consent. Eligible patients must meet the inclusion criteria.

Participants who were found eligible and completed the baseline but were not immediately randomized (due to coaching staffing issues, randomization was putting on hold at the end of 2016 and beginning of 2017), will be given an additional call to see if they are still interested in participating. Trained interviewers will use a script to 1) remind the participant of about the study and review the purpose and what is involved; 2) ask if they are still interested in participating; 3) go through the eligibility questions again if they are interested. If they are interested and found eligible, they will be mailed a baseline survey and will receive another \$20 for completion. Upon baseline return, they will be

randomized and be treated the same as all other randomized participants for the duration of the study.

- If eligible, the participant will receive the baseline survey in the mail. Once they return the baseline survey, a chart review will determine if they are eligible, and if so, the subject will be randomly assigned to the Usual Care (UC) or Intervention condition. We will continue to contact patients until we have our required sample of 500 eligible patients (250 to each arm). Intervention participants will be mailed an introductory letter, informational brochure, and Veteran's Workbook (to be used during coaching sessions) shortly before being called to schedule their first counseling session. Patients in the UC condition will receive an informational brochure. Recruitment (via the administration of a brief telephone screening questionnaire), baseline, 3 and 6-month surveys, and telephone coaching will be conducted at the Minneapolis VA. The study coordinator and/or research assistants will attempt to call the participants for a maximum of 3 times at different times of the day at each of the recruitment and data collection timepoints (eligibility, baseline, 3-month, and 6-month).
- **Describe materials that will be used to recruit subjects, e.g., advertisements. Include materials as an appendix or separate attachment.**

See IRB supporting documents

Subject payments:

- Survey participants will be compensated for their time with \$20 for each outcome assessment (baseline, 3 and 6 month) completed (for a total of \$60, or potential \$80 total if the participant is asked to complete the baseline a second time). Focus group participants will be compensated for their time with \$50. Phase 2 Pilot participants will be compensated \$20 for session 1 and 6, and \$15 for sessions 2, 3, 4 and 5. This payment amount is similar to those used in other studies, and is provided for the time and inconvenience of participating in research. The amount is not so much that subjects would feel coerced into participation.
- The study coordinator will dispense payments for survey participants for all phases.
- Phase 1 will consist of a onetime payment of a \$50 check mailed 8-10 weeks after participation in the focus group.
- In Phase 2, participants will receive a \$20 check within 8-10 weeks of completing the baseline, 3 and 6-month follow-up survey.

5.3 Informed Consent Procedures

Phase 1 & 2: We are seeking a waiver for screening pain participants at the Atlanta VA so that we can identify our population and conduct future analyses for non-

respondents. This waiver would only apply toward secondary data (i.e. data that has been collected and provided in VA records).

Phase 1 (Focus group): We will provide a full written informed consent and HIPAA authorization form.

Phase 2 Pilot: We will mail participants the recruitment letter and information sheet explaining that they can voluntarily consent by agreeing to participate in the study.

Phase 2 (Intervention): We are requesting a waiver of documentation of informed consent as recruitment and consent will be obtained verbally over the phone. We will conduct a 12-question screening phone survey to determine eligibility status for recruitment with potential subjects, and once eligible and agree to participate, all contacts are done over the phone or by mail (screening survey, baseline, 3- and 6-month follow-up survey).

- **Documentation:**
 - **Phase 1:** We will provide a full written informed consent and HIPAA authorization form.
 - **Phase 2 Pilot:** We have a waiver of documentation of informed consent, and a waiver of HIPAA authorization for the duration of the study
 - **Phase 2:** We have a waiver of documentation of informed consent, and a waiver of HIPAA authorization for the duration of the study. The study and consent will be explained over the phone after the subject meets eligibility and is interested in participation.
- [name] will conduct the focus groups at the Atlanta VA. She will review the informed consent and HIPAA with participants and obtain consent at the time of the focus group.

5.4 Inclusion/Exclusion Criteria

- **Phase 1 (Focus group participants):** The recruitment sample for focus groups will be restricted to black patients from the Atlanta VAMC, with diagnoses of hip, knee, or back pain, using algorithms derived from 14 ICD9 codes (and ICD10 code conversions) that capture the most commonly used chronic pain codes. They will then be excluded from the study intervention sample. Focus groups are restricted to black patients because the study is designed to increase walking among this population and we want to make sure that our materials are culturally appropriate. Additionally, these veterans will help us refine the recruitment materials (recruitment letter, brochure, and recruitment scripts), counselor communication strategies and pedometer instructions, and identify additional information on barriers to walking.

- **Phase 2 Pilot:** The recruitment sample will be restricted to African American patients from the Atlanta VAMC with hip, knee, or back pain (using algorithms derived from 14 ICD9 codes and ICD10 code conversions), have pain duration of ≥ 6 months, moderate-severe pain intensity and interference with function (defined as a PEG score of ≥ 5), self-reported ability to walk at least 1 block, and must be able to communicate effectively by telephone (no cognitive disability). We will not exclude patients who are on medication or receiving interventions to treat their chronic pain. We will exclude those who cannot obtain the threshold level of steps (400 steps per day) in 2 days of data collection. We will exclude Phase 2 pilot participants from the Phase 2 study.
- **Phase 2:** The recruitment sample will include all patients from the Atlanta VAMC, regardless of race/ethnicity, with hip, knee, or back pain (using algorithms derived from 14 ICD9 codes and ICD10 code conversions), have pain duration of ≥ 6 months, moderate-severe pain intensity and interference with function (defined as a PEG score of ≥ 5), self-reported ability to walk at least 1 block, and must be able to communicate effectively by telephone (e.g., no cognitive disability). We will not exclude patients who are on medication or receiving interventions to treat their chronic pain. We have chosen the Atlanta VAMC because it has a high percentage of black patients (43%).
- We will include the approximately 10% of patients who have no race data; race data will be collected on the brief screening survey.

We will not include any vulnerable populations or those who meet any of the following exclusion criteria that may interfere with the outcome assessment: a) moderately severe cognitive impairment defined as > 2 errors on a brief cognitive screener; b) anticipated back, knee, hip, or other major surgery within the next 6 months; c) patients who say they are unable to walk at least a block; d) patients who say they would be unavailable to participate in a 6 month study; e) patients with active psychotic symptoms, suicidality, severe depression, and/or active manic episode or poorly controlled bipolar disorder, as determined by chart review.

5.5 Study Evaluations

- **Describe all evaluations to be conducted (including screening; tests/questionnaires that will be administered; any procedures that subjects will be required to complete) and data collection methods. Include materials as an appendix or separate attachment.**
- See IRB supporting documents

5.6. Data Analysis

Phase 1

- **Analysis of focus group data.** Our short timeline for refining the intervention content will require us to identify key insights from our focus groups quickly so that we can use them to guide our revisions on the materials. We will therefore employ rapid assessment process (RAP) methodology to analyze the data collected in this study. RAP is a team-based method that can be used to obtain rich qualitative results in a brief amount of time. A key feature of this method is iterative data collection and analysis where investigators analyze data after each interview. For our study, use of RAP methods will involve scheduling time immediately following each focus group for the investigators participating in data collection ([name] and RAs) to identify and discuss key findings. The list of key findings will be updated and expanded with each subsequent focus group session. Investigator notes from each interview session will be amended to this list of key findings to create a running log of key interview data. The log will be periodically distributed to investigators and discussed during ongoing project meetings.
- **Phase 2 Pilot Data:** There will be no data analysis for Phase 2 Pilot. Although we will be audio-recording the counseling sessions, we plan to use these recordings ONLY to accurately capture the Veteran's reactions to the materials and counseling. We may refer back to the feedback from the Veteran in order to improve our training materials for our counselors, but will not be analyzing the recordings.

Phase 2

- The overall design of the study is a two-arm patient-level randomized trial. All analyses will take this design structure into account and will primarily follow an intent-to-treat analysis where patients are analyzed based on the group they were randomized to regardless of whether or not they actually receive the assigned intervention. Secondary analyses will assess the impact of the intensity of intervention compliance on outcomes and to test study outcomes among patients.
- **Primary Aim.** To test the hypothesis that the intervention will improve chronic pain-specific physical functioning—the primary outcome (H1a), improve emotional functioning, pain intensity and ratings of overall improvement (H1b), and increase walking (H1c), compared to UC for black patients with chronic hip, back, and knee pain.
- The primary analyses for these aims will be conducted in the sample of black patients, so the focus of much of the methods speaks to this primary sample. However, it needs to be clear that the study is designed to be adequately powered to detect effects separately in both the black and non-black groups. This is important from an implementation standpoint since if this intervention is successful it will be important to know whether the effects generalize to a non-black population.

- General Analytic Approach.** These analyses will proceed in three phases. In the first phase (data verification), we will examine the distribution of all study variables to assess extreme values, missing data, variances, skewness, and type of distribution. Frequency distributions and descriptive statistics for all study variables will be computed prior to conducting any analyses. Should normality tests indicate evidence of non-normality for any of our variables (e.g., pain severity ratings) we will compute necessary data transformations. In the second phase, we will evaluate bivariate associations between patients' experimental condition and the outcomes, as well as between each covariate and the outcomes and between each covariate and intervention. These analyses will be done to determine unadjusted measures of effect and assess possible confounders. In the final phase, we will use generalized regression models to estimate the main effects of the intervention. Because of randomization of treatment assignment, we do not anticipate any imbalances in baseline characteristics between groups, but any differences between experimental arms in baseline characteristics will be included as covariates. Likewise, if we find differences in missing data, multiple imputation methods will be used to explore the impact of the missing data and attempt to adjust for its effects on the intervention's effectiveness.
- Aims 1a) and 1b)** To compare the effects of the intervention to UC on the IMMEDIATE measures of pain outcomes. The primary measure for these aims is the RMDQ score (i.e. primarily a 30% reduction from baseline and secondarily mean change from baseline), and the other secondary measures are pain intensity, the Profile of Mood States, and the global rating of change scale. Analytic approaches for all of these measures will be similar with the exception that some of the measures are dichotomous (i.e. did the participant have a 30% reduction in RMDQ) while other outcomes are assessed on a continuous scale. For all of these outcomes we will use generalized linear regression fit using appropriate distribution and link functions (i.e. for the primary outcome of whether the patient's RMDQ improved by 30% or more we will fit a binomial distribution and logit links, whereas for the comparison of mean differences between treatment groups we might fit a normal distribution). We expect the RMDQ score to decrease (indicating improvement) in the short term (3-month) as well as over the longer term (6-month) in the intervention group, while improving only slightly from baseline in the control group. For continuous outcomes in this model, for example the RMDQ, scores from both 6 months and baseline will be used as the dependent variable, and the independent variables will include the indicator for the intervention group and an interaction term of 6-month time by intervention group indicator. Each participant will be modeled as a random intercept to allow within-patient correlation of the repeated measures. The model can also include other baseline covariates such as age and pain intensity. The use of a mixed-effects model, rather than using multiple linear regression or analysis of

covariance with change-scores or the 6-month values as the dependent variable, will allow us to use data from participants who may be missing either baseline or the 6-month data while giving an unbiased estimate of the outcome comparisons as long as missing-ness is approximately random. The 3-month effect will be similarly assessed.

- We will assess the time-averaged effect of the intervention on pain-related functional interference and the outcome trends over time using the outcome measures at all three times (including the baseline) as repeated measures nested within patients and using a mixed-effects model. Prior to fitting the mixed-effects model, we will explore the trends graphically by plotting the cross-sectional means of the outcome measures at each measurement time separately by the two study groups. We will also graph the outcome measures by individual participants to assess the participant specific longitudinal pattern over time. The mixed-effects model will be guided by the results of the graphical analyses. For instance, we expect decreasing trends in the outcome measures over time in the intervention group and no particular trends in the control group. If such a pattern is indicated, linear time and an interaction of linear time by intervention group will be included in the model. In this model, if the time variable is not significant and the interaction is estimated with a significant negative coefficient, it would provide evidence for linearly decreasing outcomes (i.e., improvement in function) in the intervention group over the one follow-up period. If, on the other hand, the graphical analyses suggest that the outcomes in the intervention group decrease at 3 months with no noticeable change between 3 to 6 months, we will model this by including time as dummy categorical variables and interaction terms of intervention group by time dummy categorical variables. An appropriate contrast for the covariate adjusted difference in outcome means at 3 months and 6 months between groups will be constructed to estimate and test for the intervention effect. Using this model, mean changes from baseline can also be estimated and tested for each group. If we find no difference in the intervention effect between 3 and 6 months using this model, we will model the post-intervention time together to obtain a time-averaged intervention effect. The mixed-effects models will also include the baseline values of the outcome measure and other baseline covariates to adjust for potential baseline differences between the groups.
- **Aim 1c)** To compare the effects of the intervention to UC on increasing walking behavior. Walking will be measured by step counts, which are reported based on readings from the Omron HJ-720 ITC pedometer. The effect of the intervention on step counts will be assessed by comparing average daily step counts (or appropriately transformed scores, if the distribution is shown to be skewed) measured over 7 days. We will use a mixed-effects model with the average daily step counts as reported on the baseline survey, during the last week of the 3 month and 6 month measurement points as the dependent variables, with a similar analytic plan as described for Aim 1a.

- **Secondary Aim 1:** To investigate whether key contributors to racial/ethnic disparities targeted by the intervention (motivation to exercise, pain/exercise efficacy, reduction of pain-related fear) mediate improvement in chronic pain outcomes and increases in walking. The key measures for this aim include the Exercise Regularly Scale, the PSEQ-8, and the FABQ Scale 1. Each of these will be measured at baseline, 3- and 6-month, and each has continuous distribution, and therefore, analytic approaches for each of these measures will be identical to that of Primary Aim 1 with the primary objective of assessing the long-term (6-month) effect of the intervention on these outcomes and secondary objective of exploring outcome trends over time. Indirect effects will be directly tested using the bootstrap approach to obtaining confidence intervals to avoid the often-violated assumption underlying Sobel's (1982) method that the sampling distribution of the indirect effect be normal.¹⁰³
- **Secondary Aim 2:** To explore whether the intervention reduces service utilization and use of opioid analgesics. Using similar analytical methods as described for the Primary Aims, we will use generalized linear models to explore whether service utilization and use of opioid analgesics measures are reduced in the intervention group compared to the UC group.
- **Secondary Aim 3:** To determine if the intervention is effective for non-black VA patients and other subgroups of patients who may experience barriers to effective pain treatment. We will conduct the same analyses as for the Primary Aims and Secondary Aims 1-2 on the sample of non-black patients (most of whom are expected to be white) and subgroups based on key demographic factors (age, gender, education, and income) and psychological, environmental, and utilization, measured at the baseline survey, that we included because they were expected to constitute barriers to effective pain treatment, based on our theoretical framework. We will also explore whether treatment effects will be moderated by common psychiatric conditions (PTSD, anxiety, depression) and receipt of other forms of pain treatment, in order to see whether our intervention is effective for Veterans with these common psychiatric conditions and/or who are involved in other pain treatment.
- **Secondary Aim 4:** To explore whether the intervention reduces racial disparities in pain outcomes, generalized linear regression models described above do allow for the incorporation of a race by intervention variable into the models to explore whether there might be evidence that the intervention is more or less in effective in black Veterans as compared with non-black Veterans. We expect that the intervention will be effective across racial groups and assume that the differences between racial groups receiving the intervention will be substantially smaller than the differences between the intervention and UC groups. Since the study is powered to detect the main effects that are assumed to be larger than

the interaction effects, this study may not be able to detect clinically important differences in the intervention's effectiveness between racial groups. We will however explore tests of interaction for the key study outcomes and use any information to help craft a future study, if we find evidence that there might potentially be important race-specific treatment effects.

- **Describe how, where and by whom the data will be analyzed.**

The data will be analyzed at CCDOR by statisticians and Co-Investigators, including [name], [name], [name], and [name] at the Minneapolis HCS.

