Our sample size calculation was based using the Roland Morris Disability Questionnaire (RMDQ) score as the primary endpoint. For our primary analysis we use a responder analysis, in which we define clinical significant changes as a 30% reduction in pain disability from baseline, using the RMDQ, and have powered the study to be able to detect this change. This is the accepted threshold for clinically significant improvement in clinical trials and recommended by the IMMPACT guidelines and studies demonstrate that a 30% reduction on the RMDQ is a clinically important difference.^{96,97} Prior studies have shown that 15-20% of usual care patients will demonstrate a 30% reduction in pain function score (using the RMDQ and similar measures) from baseline to follow-up, so in order to detect an absolute difference to 20% in the primary outcome measure between treatment groups (i.e. 15-20% in the usual care group compared with 35-40% in the intervention group), we estimate that we will need between 86-97 people in each group with complete data. This estimate takes into account that we are setting the alpha error rate to look separately at both black and non-black patients. We will use the between-group change on the RMDQ as a secondary measure.

We also need to factor in that up to 50% of the study sample may be non-black, since we want to be able to have power to detect meaningful effects in the subgroup that only includes black patients (~100/50%=200). To allow for up to 20% attrition, we would need to randomize 250 patients for each arm of the study, for a total of 500 patients recruited, and 200 black patients with complete data for the final analyses. We estimate that in order to reach a total of 500 patients randomized, we will need to enroll (i.e. participants who are eligible after the phone screener is completed and are thus mailed a baseline survey packet) as many as 1500 patients. Once we reach the goal of randomizing 500 participants, we will stop enrollment.

Risk vs. Potential Benefit

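### Covariates for the primary responder model are chosen by observed baseline imbalance, with no cut-off or list; a short list fixed before arms are compared would be better at almost no cost

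*Combined protocol and SAP*

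**What the plan says.** All references are to the combined protocol and SAP.

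- **Section 5.6, General Analytic Approach.** The analysis has three phases. The second looks at arm against outcome, each covariate against outcome, and each covariate against arm: "These analyses will be done to determine unadjusted measures of effect and assess possible confounders". The third fits the regression models for the main effects. The covariate rule for those models is one sentence. It opens with "Because of randomization of treatment assignment, we do not anticipate any imbalances in baseline characteristics between groups" and continues that "any differences between experimental arms in baseline characteristics will be included as covariates".
- **Section 5.6, Aims 1a) and 1b).** For the primary outcome, a 30% RMDQ reduction, "we will fit a binomial distribution and logit links". No covariates are listed for it. In the account of the continuous, random-intercept model comes the sentence "The model can also include other baseline covariates such as age and pain intensity".
- **Same aims, mixed-effects models over time.** These include the outcome's baseline value and "other baseline covariates to adjust for potential baseline differences between the groups", which are not named.
- **Section 5.1, Environmental Factors.** Season is to be taken into account from the survey date. No model is named.
- **Section 5.6, Secondary Aim 3.** "We will conduct the same analyses as for the Primary Aims and Secondary Aims 1-2 on the sample of non-black patients".

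**The concern.** The imbalance sentence is the only covariate rule that clearly reaches the primary model, and it leaves that model undefined. It does not say what counts as a difference, which characteristics are examined, or whether balance is judged within each race group. Its own opening clause expects no imbalance because of randomisation, so whatever appears is chance. Selecting on chance imbalance does not favour the covariates that predict response. Baseline RMDQ, from which the responder outcome is calculated, enters the primary model only if it happens to differ between arms.

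Two things are at stake: freedom in the primary model once arms have been compared, and precision that a few well-chosen baseline variables could add in about 200 black patients with complete data.

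**Working it through.** **1. The plan's own sample size.** Inputs from Power and sample size (5.1): 15-20% response under usual care and 35-40% under intervention. Alpha and power are not given as numbers. I assume two-sided 0.025 (0.05 split over two race groups) and 80%. With the pooled formula, n = [z(α)·√(2p̄q̄) + z(power)·√(p₁q₁+p₂q₂)]² / δ²:

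- 15% v 35%: (2.241×√0.375 + 0.842×√0.355)² / 0.04 = 88
- 20% v 40%: (2.241×√0.42 + 0.842×√0.40)² / 0.04 = 99

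The unpooled formula gives 85 and 96. The stated 86-97 lies between the two, so it is reproduced. Then 100/0.5 = 200 and 200/0.8 = 250 per arm, as stated. At 100 per arm, unadjusted power for 20% v 40% is 80.7%.

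**2. How many covariates the rule could select.** Assume 20 candidates and 100 per arm.

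- p<0.05: 20×0.05 = 1 on average. If the candidates are independent, the chance of at least one is 1−0.95²⁰ = 64%.
- p<0.20: 20×0.20 = 4.
- Standardised difference above 0.1: P(|Z| > 0.1/√(2/100)) = 0.4795, and 20×0.4795 = 9.6.

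All three comply with the text.

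**3. Power, imbalance judged at p<0.05.** Logistic simulation with 5000 replicates (Monte Carlo error about 0.56 points), 100 per arm, 20% v 40%, alpha 0.025. There are 20 correlated baseline measures, with PEG truncated at 5 or more to match eligibility (assumed RMDQ-PEG correlation 0.50 before truncation, 0.37 after). Prognostic strengths are assumptions. Figures are percentages.

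| Log-odds per SD (RMDQ, PEG, age) | Unadjusted | Rule, black patients | Rule, both race groups together | Fixed three | Fixed − rule (black patients) | Fixed − unadjusted |
|---|---|---|---|---|---|---|
| 0, 0, 0 | 80.2 | 79.3 | 80.0 | 79.8 | 0.5 | −0.4 |
| 0.2, 0.2, 0.2 | 80.1 | 79.2 | 79.7 | 81.3 | 2.1 | 1.2 |
| 0.3, 0.3, 0.3 | 80.5 | 80.0 | 80.5 | 83.3 | 3.3 | 2.8 |
| 0.3, 0, 0 | 80.8 | 79.8 | 80.5 | 81.3 | 1.5 | 0.5 |
| 0.4, 0.2, 0.1 | 80.3 | 79.9 | 80.1 | 82.6 | 2.7 | 2.3 |
| 0.6, 0, 0 | 81.1 | 80.5 | 80.9 | 83.6 | 3.1 | 2.5 |

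If balance is judged in both race groups together, the gain over the rule runs from −0.2 to 2.8 points.

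**4. Power by cut-off (separate run).**

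| Log-odds per SD | p<0.05 | p<0.20 | Std. diff. >0.1 | Fixed three | Fixed − rule |
|---|---|---|---|---|---|
| 0, 0, 0 | 80.1 | 78.6 | 78.3 | 80.8 | 0.7 / 2.2 / 2.5 |
| 0.3 each | 80.3 | 79.7 | 80.1 | 83.0 | 2.7 / 3.3 / 2.9 |
| 0.6, 0, 0 | 80.1 | 80.0 | 79.8 | 83.5 | 3.4 / 3.5 / 3.7 |

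Fixed adjustment with no prognostic value gave 79.8 in one run and 80.8 in the other, so gaps below about 1 point show nothing. A further run of 3000 replicates, with RMDQ and PEG acting in opposite directions, gave 81.9% fixed against 77.8-79.1% under the rule, a gap of 2.8-4.1.

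Stronger prognosis would give more. With 15 independent candidates, three of them prognostic at 0.5 or 0.7 per SD, fixed adjustment reached about 86% and 89% against 81-82% under the rule and 82% unadjusted. Nothing in the documents supports strengths that large, so I do not rely on them.

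**5. Type I error.** At each single cut-off, rejection under the null was 2.1-2.7% across the runs, against 2.5% nominal. Reporting the most favourable of the unadjusted result and three cut-offs rejected 3.0-3.2% in one set of runs and 4.0% in another.

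**6. Effect estimate.** The mean log-odds ratio was 0.99-1.00 unadjusted, 1.00-1.01 under the rule at p<0.05, and 1.01-1.09 with the fixed list. At a standardised difference above 0.1 (0.3 each) the rule gave 1.09. The standardised risk difference stayed at 0.199-0.201.

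**The case against.** - **The plan screens covariates against outcomes too.** It may intend covariates that are both imbalanced and related to outcome. That is a possible intention, but the operative sentence selects on differences between arms alone. The dual reading would still need a cut-off and a list, and it was not simulated.
- **Covariates are named elsewhere.** Season is a firm commitment without a model. Age and pain intensity could be carried over to the logistic model, because the plan calls its approaches similar across outcome types, but they remain optional. None of this fixes the primary model.
- **The race-group question has a natural answer.** The methods are written for black patients and then repeated in non-black patients, so balance is most likely judged within each group. I accept that. It also means the two groups could be adjusted for different covariates.
- **The direction of baseline RMDQ is unknown.** Response is a percentage fall from baseline. Follow-up scores generated under assumed values (baseline mean 12-14, SD 5, residual SD 4-5) gave log-odds per SD from −0.6 to +0.4, passing through zero. Near zero, RMDQ adds little. Opposite signs did not remove the gain over the rule.
- **The unadjusted result is already planned, with power of 80-81%.** True, and it limits the harm.

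A reader might infer that the rule inflates type I error. It does not at any single cut-off. The 3.0-4.0% arises only if several versions are tried and the best reported, and nothing in the documents suggests that. A reader might also infer that outcomes drive the covariate choice. The text does not say so. Arm against covariate and arm against outcome are examined in the same phase, and only the model fit comes later.

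**Conclusion.** The point holds as a cheap improvement, not as an error that invalidates the analysis or the sample size. The primary logistic model has no fixed covariates, and the rule that fills the gap is undefined and driven by chance. A fixed list would gain roughly 1-4 points of power over the rule. Over the unadjusted test it would gain about 0-4 points, and nothing if the covariates are not prognostic. Even without prognostic value the rule can cost a little, because loose cut-offs load the model with useless covariates. These sizes depend on the assumed prognostic strengths, 20 candidates, alpha of 0.025 and 100 per arm. The lack of a defined rule depends on none of them.

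**What to change.** In section 5.6:

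1. State that the primary logistic model always adjusts for a short list fixed before arms are compared, whatever the observed balance, for example baseline RMDQ, PEG and age. Say whether season is on the list.
2. Use the same list in black and non-black patients, and for the unnamed covariates of the mixed-effects models.
3. Keep the imbalance rule as a sensitivity analysis, with its cut-off and candidate set stated.
4. Report the unadjusted result, already planned, alongside.

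The cost is plan wording and slight extra analysis. Table 3 has RMDQ and PEG at baseline, birthdate comes from the CDW, and section 5.2 has the baseline survey returned before randomisation. With no prognostic value, fixed adjustment showed no loss beyond simulation error (79.8% against 80.2%).

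The small downside is that the odds ratio becomes conditional on the list. A standardised risk difference with confidence interval may be added. It would match the sample size reasoning, which was set "in order to detect an absolute difference to 20% in the primary outcome measure between treatment groups", but it is optional and not needed to settle this point.
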